2.0/ February 20, 2015/ PPD [Redacted]	
Status of survey: Ongoing
 
2.1. Study Design Planned survey period Modification associated with a change in the survey plan
 
5.2. Efficacy analysis set Patients with clinical evaluations data collected were additionally included in the efficacy analysis set.
 
6.1. Safety endpoints Suicide-related events were added.
 
7. Handling of missing data Modified to exclude efficacy evaluation from Appendix “Definition of visit schedule”. Specified that missing data will not be imputed for clinical efficacy.
 
8.2.3.1. Adverse reactions Tabulation of suicide-related events was added.
 
8.2.4.2. Pain score 8.2.4.3. Sleep interference score 8.2.4.4. PGIC 8.2.4.5. CGIC Modified to exclude from Appendix “Definition of visits”.
 
A1.1 Data to be used for tabulation and analysis The scope of data to be used was specified.
 
A1.2 Definition of visit schedule Addition of the definition of Visit 1 and modification associated with the addition Handling of multiple observation data collected within the same visit window was additionally specified.
 
A.2.1 Subgroup analysis Reference population for calculation of risk ratio and risk difference as subgroup analyses of safety and efficacy was additionally specified.
 
Others Description adjustment

090177e18ef7c5fa\0.1\Draft\Versioned On:18-Jul-2018 10:23 (GMT)

Version/ Date/ Author(s)	Summary of Changes/Comments
3.0/ February 17, 2016 PPD [Redacted]	
Status of survey: Ongoing
 
5. Analysis sets Handling of patients unable to be resurveyed was changed.
 
6.1. Safety endpoints Definitions of major investigation items were additionally specified.
 
8.2.3.4. Subgroup analysis Tabulation to evaluate the relationship between patient demographics, etc. and the development of adverse reactions associated with long-term use was added.
 
Others Description adjustment

4.0/ February 17, 2017/ PPD [Redacted]	
Status of survey: Ongoing
 
6.1. Safety endpoints Euphoric mood-related events were added as other safety endpoints. Evaluation of adverse events was added for suicide-related events. Laboratory parameters to be assessed as a population, and laboratory parameters to be assessed were added.
 
8.2.3.1. Adverse reactions Tabulation of major investigation item of peripheral edema and edema-related events was added. Tabulation of the relationship between dosage and administration and development of adverse reaction and the relationship between prior and concomitant medications and development of adverse reactions was added.
 
8.2.3.3. Other endpoints Body weight: Tabulation of adverse reactions by presence or absence of weight gain was added. Laboratory parameters: Calculation of summary statistics was added.
 
8.2.3.4. Subgroup analysis Calculation of summary statistics of laboratory parameters was added for patients whose target disease is painful diabetic neuropathy.
 
8.2.4.1. Clinical efficacy Definition (equation) of response rate was added.
 
A1.1 Data to be used for tabulation and analysis Handling of efficacy-related data was additionally specified.
 
A1.2 Definition of visit schedule Laboratory parameters were added to endpoints.
 
Others Description adjustment

090177e18ef7c5fa\0.1\Draft\Versioned On:18-Jul-2018 10:23 (GMT)

Version/ Date/ Author(s)	Summary of Changes/Comments
5.0/ July 28, 2017 PPD [Redacted]	
Status of survey: Ongoing
 
5.4. Subgroup Inpatient/outpatient status at the initial prescription, past medical history and complications were added for subgroup analysis of efficacy.
 
6.1. Safety endpoints Handling of serious adverse reactions or adverse events was specified. Pancreas-related events, thyroidal function-related events, change in appetite and activity-related events, and withdrawal symptom and rebound phenomenon-related events were added as other safety endpoints.
 
8.1.1. Analysis of continuous data Method of analysis of covariance was added.
 
8.2.2. Patient demographics and treatment history Tabulation of pain score (continuous data) was added as patient demographics. Tabulation of daily dose (continuous data) and final daily dose was added as information on administration of Lyrica.
 
8.2.3.1. Adverse reactions Tabulation of pancreas-related events, thyroidal function-related events, change in appetite and activity-related events, and withdrawal symptom and rebound phenomenon-related events was added. Tabulation of patients with special background was added.
 
8.2.4.6. Subgroup analysis (efficacy) Analysis of response rate of clinical efficacy was changed to analysis of pain score based on analysis of covariance model.
 
A.2.1 Subgroup analysis Modification associated with changes in 8.2.4.6. Subgroup analysis.
 
Others Description adjustment

090177e18ef7c5fa\0.1\Draft\Versioned On:18-Jul-2018 10:23 (GMT)

Version/ Date/ Author(s)	Summary of Changes/Comments
6.0/ December 26, 2017/ PPD [Redacted]	
Status of survey: Survey completed
 
6.1. Safety endpoints Skin disorder-related events were added.
 
8.2.1. General description of patients Modified to conduct the safety analysis set only in the tabulation by timing in the summary of discontinuation and dropouts.
 
8.2.2. Patient demographics and treatment history Details of the method of tabulation of daily dose (continuous data) were added as the information on administration of Lyrica.
 
8.2.3.1. Adverse reactions Modified to review the definition of major investigation item of peripheral edema and edema-related events to be used for detailed investigation. Tabulation of skin disorder-related events was added. Taking accumulated number of patients into consideration, scope of tabulation by target disease (i.e., diagnosis of neuropathic pain) was added to evaluate the relationship between prior and concomitant medications and development of adverse reactions.
 
8.2.3.4. Subgroup analysis (safety) Added tabulation to be performed based on factors showing a significant difference by testing to evaluate the relationship between patient demographics, etc. and development of adverse reactions.
 
Listings Listing of events of major investigation items was deleted (the European risk management plan should be referred to as necessary because events to be handled as major investigation items are defined as Safety Specification in the European risk management plan of Lyrica).
 
Others Description adjustment

7.0/ February 13, 2018/ PPD [Redacted]	
Status of survey: Survey completed
 
8.2.3.1. Adverse reactions For patients with special background, pediatric patients were additionally specified and tabulation of serious adverse reactions was added.
 
8.2.3.4. Subgroup analysis (safety) Added tabulation to be performed based on factors showing a significant difference by testing to evaluate the relationship between patient demographics, etc. and development of adverse reactions.
 
8.2.4.6. Subgroup analysis (efficacy) Added tabulation to be performed based on factors showing a significant difference by testing to evaluate the relationship between patient demographics, etc. and efficacy.
 
Others Description adjustment

090177e18ef7c5fa\0.1\Draft\Versioned On:18-Jul-2018 10:23 (GMT)

Version/ Date/ Author(s)	Summary of Changes/Comments
8.0/ March 9, 2018 PPD [REDACTED]	Status of survey: Survey completed 6.1. Safety endpoints Accident-related events were added as other safety endpoints. 8.2.3.4. Subgroup analysis (safety) Added tabulation to be performed based on factors showing a significant difference by testing to evaluate the relationship between patient demographics, etc. and development of adverse reactions.

2. Introduction

This statistical analysis plan describes a plan of statistical analysis to be performed in the special investigation of Lyrica® Capsule (hereinafter referred to as Lyrica). In this plan, sentences cited from the protocol are shown in *italic*.

2.1. Study design

Study population

- *Indication: Neuropathic pain*
- *Dosage and administration: The usual starting dose in adults is 150 mg/day of pregabalin orally administered in 2 divided doses, which may be gradually increased to 300 mg/day over one week or longer. The dose may be adjusted depending on age and symptoms as appropriate, provided the daily dose may not exceed 600 mg and Lyrica should be orally administered in 2 divided doses regardless of the daily dose.*
- *Study population: The survey covers the patients satisfying all of the following requirements:*
 - *Patients who are registered in the drug use investigation of Lyrica and are still on treatment with Lyrica after Week 13*

Observation period

The observation period of this survey will occur in succession to the 13-week observation period of the drug use investigation. It will start from Week 14 and last until Week 104 (Day 728 from the start of treatment counted as Day 1). However, in cases where treatment has been completed or discontinued before Week 104, observation will continued until completion (discontinuation) of treatment, and follow-up will be made for one week (7 days) after completion (discontinuation) of treatment.

During this survey, safety will be evaluated on the day of the first visit after Week 26, Week 52, Week 78, and Week 104 (including the last day of each observation period), as a rule. In cases where treatment has been completed or discontinued, safety will be evaluated until the day of the first visit following 7-day period after the completion (discontinuation) of treatment, and safety information will be collected for this period.

Completion of treatment means cases where further treatment with Lyrica is judged unnecessary because of achievement of the purpose of treatment set at the start of treatment (e.g., cure of target diseases).

During the observation period, the survey forms will be collected at Week 26, Week 52, Week 78, and Week 104.

Planned survey period

Survey period : April 2011 to April 2017
Registration period : April 2011 to August 2016

Target sample size and rationale

The target sample size is 310 patients who have been treated for at least 52 weeks and for 104 weeks at most.

Aiming at appropriate investigation of safety and efficacy of Lyrica during long-term use, the target sample size was set at 310, which is expected to have a 95% or higher probability to detect adverse reactions occurring at the incidence of 1% (0.97%) or higher in at least one patient.

A total of 310 patients with neuropathic pain who have been examined in the observation period of at least 52 weeks will be collected.

2.2. Study objective

The objective of this survey is to evaluate the safety and efficacy of long-term use of Lyrica in routine clinical practice.

The following events will be evaluated as major investigation items;

- Peripheral edema and edema-related events**
- Dizziness, somnolence, loss of consciousness, syncope, and potential for accidental injury*
- Vision-related events*

**: Adverse events of the cardiovascular and respiratory systems will also be checked.*

3. Interim and final analyses

Interim analyses for periodical safety report will be regularly performed in this survey. Interim analyses will be performed only for items necessary for periodical safety report as

specified in this plan. In addition, the final analysis for the application for reexamination will be performed. At the final analysis, all analyses specified in this plan will be performed.

4. Hypothesis and decision rule

4.1. Statistical hypothesis

Because this survey is not a confirmatory investigation, the testing should be considered as exploratory in nature. Unless otherwise specified, the 2-sided testing is performed with a significance level of 5%.

4.2. Statistical decision rule

Not applicable.

5. Analysis sets

For analysis of registered patients of the survey, data collected in the preceding drug use investigation and this survey will be used.

5.1. Safety analysis set

The safety analysis set is the full analysis set that is as close to all patients treated with Lyrica as possible. More specifically, the safety analysis set is defined as the population of registered or reported patients, excluding those who meet any of the following conditions.

- a. The survey form could not be collected at all (description in the report: “survey form not collected”).
- b. There was a contract violation or deficiency (description in the report: “contract violation/deficiency”).
- c. There was a registration violation (description in the report: “registration violation”).
- d. Administration of Lyrica under survey has not been reported at all (description in the report: “no administration information”).
- e. Information on adverse events has not been reported at all - no visits after the day of initial prescription (description in the report: “no adverse event information - no revisit”).
- f. Information on adverse events has not been reported at all - adverse events not described (description in the report: “no adverse event information - not described”).

Detailed handling of patient inclusion in/exclusion from the analysis set should be in accordance with patient inclusion/exclusion criteria separately specified.

5.2. Efficacy analysis set

The efficacy analysis set is defined as the population excluding patients meeting any of the following conditions from the safety analysis set.

- a. Efficacy evaluations have not been reported at all (description in the report: “no efficacy information”).
- b. Non-target disease of the survey (description in the report: “non-target disease”)

Detailed handling of patient inclusion in/exclusion from the analysis set should be in accordance with patient inclusion/exclusion criteria separately specified.

5.3. Other analysis sets

Not applicable.

5.4. Subgroups

Subgroup analyses of safety will be performed for the following patient demographics and other factors.

- Hepatic impairment
- Renal impairment
- Children (<15 years), adults (≥15 to <65 years), elderly (≥65 years)
- Age [<65 years, ≥65 to <70 years, ≥70 to <75 years, ≥75 to <80 years, ≥80 to <85 years, ≥85 years]
- Sex [male, female]
- Inpatient/outpatient status at the initial prescription [inpatient, outpatient]
- Body weight at the start of treatment (by sex) [<40 kg, ≥40 to <50 kg, ≥50 to <60 kg, ≥60 kg]
- Name of target disease (i.e., diagnosis of neuropathic pain) [by disease name]
- Hemodialysis [no, yes]
- Creatinine clearance [<15 mL/min, ≥15 to <30 mL/min, ≥30 to <60 mL/min, ≥60 mL/min]
- Past medical history [no, yes]
- Complications [no, yes]
- Prior medications [no, yes]
- Concomitant medications [no, yes]
- Non-medication therapies [no, yes]
- Timing of drug administration (at the start of treatment) [before meal, after meal, other]
- Daily dose (at the start of treatment) [≤25 mg, >25 to ≤75 mg, >75 to ≤150 mg, >150 to ≤300 mg, >300 to ≤600 mg, >600 mg]

- Daily dose (maximum) [≤ 25 mg, >25 to ≤ 75 mg, >75 to ≤ 150 mg, >150 to ≤ 300 mg, >300 to ≤ 600 mg, >600 mg]
- Pregnant and parturient women (pregnant)

Subgroup analyses of efficacy will be performed for the following patient demographics and other factors.

- Hepatic impairment
- Renal impairment
- Children (<15 years), adults (≥ 15 to <65 years), elderly (≥ 65 years)
- Age [<65 years, ≥ 65 to <70 years, ≥ 70 to <75 years, ≥ 75 to <80 years, ≥ 80 to <85 years, ≥ 85 years]
- Sex [male, female]
- Inpatient/outpatient status at the initial prescription [inpatient, outpatient]
- Body weight at the start of treatment (by sex) [<40 kg, ≥ 40 to <50 kg, ≥ 50 to <60 kg, ≥ 60 kg]
- Name of target disease (i.e., diagnosis of neuropathic pain) [by disease name]
- Hemodialysis [no, yes]
- Creatinine clearance [<15 mL/min, ≥ 15 to <30 mL/min, ≥ 30 to <60 mL/min, ≥ 60 mL/min]
- Past medical history [no, yes]
- Complications [no, yes]
- Prior medications [no, yes]
- Concomitant medications [no, yes]
- Timing of drug administration (at the start of treatment) [before meal, after meal, other]
- Daily dose (at the start of treatment) [≤ 25 mg, >25 to ≤ 75 mg, >75 to ≤ 150 mg, >150 to ≤ 300 mg, >300 to ≤ 600 mg, >600 mg]
- Daily dose (maximum) [≤ 25 mg, >25 to ≤ 75 mg, >75 to ≤ 150 mg, >150 to ≤ 300 mg, >300 to ≤ 600 mg, >600 mg]

6. Endpoints and covariates

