8.1.3. Analysis of binary data

Frequency and its proportion will be calculated. If the confidence interval of proportion is calculated, a 2-sided 95% confidence interval (exact method) will be calculated.

If the proportion is compared between subgroups, Fisher’s exact test and Cochran-Armitage test (exact method) will be performed for the relationships with nominal scale data and

ordinal scale data, respectively, and the risk ratio and risk difference with their 95% confidence intervals will be calculated.

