- Timing of drug administration (at the start of treatment) [before meal, after meal, other]
- Daily dose (continuous data)
- Daily dose (at the start of treatment) [≤ 25 mg, >25 to ≤ 75 mg, >75 to ≤ 150 mg, >150 to ≤ 300 mg, >300 to ≤ 600 mg, >600 mg]
- Daily dose (maximum) [≤ 25 mg, >25 to ≤ 75 mg, >75 to ≤ 150 mg, >150 to ≤ 300 mg, >300 to ≤ 600 mg, >600 mg]
- Daily dose (final) [≤ 25 mg, >25 to ≤ 75 mg, >75 to ≤ 150 mg, >150 to ≤ 300 mg, >300 to ≤ 600 mg, >600 mg]

Dosing period is from the day of initial dose in the survey to the day of last dose, including period of dose interruption. Daily dose (continuous data) will be calculated as the mean dose during the entire period in which Lyrica was actually administered to each patient excluding pro re nata (PRN) prescription, and the mean, standard deviation, and mode will be calculated in the safety analysis set.

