8.2.3. Safety analysis

8.2.3.1. Adverse reactions

- **All adverse reactions**

Number and proportion of patients with adverse reactions will be tabulated by SOC and PT.

- **Serious adverse reactions**

Number and proportion of patients with serious adverse reactions will be tabulated by SOC and PT.

- **Details of adverse reactions**

Number and proportion of patients with adverse reactions will be tabulated by SOC and PT for each of the following items.

- Seriousness [Serious, non-serious]
- Expected/unexpected [expected, unexpected]
- Number of days to onset [≤ 4 weeks, >4 to ≤ 13 weeks, >13 to ≤ 26 weeks, >26 to ≤ 52 weeks, >52 to ≤ 78 weeks, >78 to ≤ 104 weeks, >104 weeks]
- Action taken [discontinuation, dose interruption or reduction, dose increase]

- Outcome [not recovered, recovered with sequelae, recovering, resolved/recovered, unknown]

If the same adverse reaction (the same PT) occurs more than once in the same patient, tabulation of the number of patients experiencing the adverse reactions will be handled as follows.

- Seriousness: Serious if both serious and non-serious reactions occurred
- Expected/unexpected: Unexpected if both expected and unexpected reactions occurred
- Number of days to onset: Number of days to onset of the first reaction
- Action taken: If more than one action were taken, select one action in the following order of priority: discontinuation, dose interruption or reduction, dose increase, none
- Outcome: Outcome of the reaction lastly occurred in the patient

- **Major investigation items**

Number and proportion of patients will be calculated for the following major investigation items.

- Peripheral edema and edema-related events*^a
*: Adverse events of the cardiovascular and respiratory systems will also be checked.
- Dizziness, somnolence, loss of consciousness, syncope, and potential for accidental injury
- Vision-related events

Furthermore, number and proportion of patients with major investigation items will be tabulated for each SOC and PT by seriousness, action taken, and outcome.

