8.2.3.4. Subgroup analysis

Number and proportion of patients with at least one adverse reaction will be tabulated by factor specified in Section 5.4. Furthermore, number and proportion of patients with at least one adverse reaction occurring (initial onset) at >13 to ≤52 weeks will be tabulated and tests

specified in Section 8.1.3 will be performed to evaluate the relationship between patient demographics, etc. and development of adverse reactions associated with long-term use. Risk ratio and risk difference for the incidence of adverse reactions and their 95% confidence intervals will be calculated between subgroups.

In addition, number and proportion of patients with adverse reactions in each subgroup will be tabulated by SOC and PT for factors showing a significant difference by testing to evaluate the relationship between patient demographics, etc. and development of adverse reactions. Moreover, patient demographics, etc. (including breakdown of past medical history and complications, prior and concomitant medications) will be tabulated in each subgroup and number and proportion of patients with serious adverse reactions will be tabulated by SOC and PT in each subgroup as necessary.

Laboratory parameters will be tabulated as specified in Section 8.2.3.3 in patients whose target disease is painful diabetic neuropathy.

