10.2. Appendix 2: Details of statistical methods

A2.1 Subgroup analysis

Reference populations for calculation of risk ratio and risk difference in subgroup analyses of safety are shown below.

Factor	Category	Reference population	Safety/Efficacy
Special population			
Hepatic impairment	Yes, No	None	Safety
Renal impairment	Yes, No	None	Safety
Age	Children (<15 years), adults (≥15 to <65 years), elderly (≥65 years)	Adults (≥15 to <65 years)	Safety
Patients demographics and others			
Sex	Male, female	Male	Safety
Age	<65 years, ≥65 to <70 years, ≥70 to <75 years, ≥75 to <80 years, ≥80 to <85 years, ≥85 years	<65 years	Safety
Inpatient/outpatient status at the initial prescription	Inpatient, outpatient	Outpatient	Safety
Body weight (by sex)	<40 kg, ≥40 to <50 kg, ≥50 to <60 kg, ≥60 kg	≥50 to <60 kg	Safety
Name of target disease [by disease name]		N/A	N/A
Hemodialysis	Yes, No	None	Safety
Creatinine clearance	<15 mL/min, ≥15 to <30 mL/min, ≥30 to <60 mL/min, ≥60 mL/min	≥60 mL/min	Safety
Past medical history	Yes, No	None	Safety
Complications	Yes, No	None	Safety
Prior medications	Yes, No	None	Safety
Concomitant medications	Yes, No	None	Safety
Non-medication therapies	Yes, No	None	Safety
Timing of administration (at the start of treatment)	Before meal, after meal, other	After meal	Safety
Daily dose (at the start of treatment)	≤25 mg, >25 to ≤75 mg, >75 to ≤150 mg, >150 to ≤300 mg, >300 to ≤600 mg, >600 mg	>75 to ≤150 mg	Safety
Daily dose (maximum)	≤25 mg, >25 to ≤75 mg, >75 to ≤150 mg, >150 to ≤300 mg, >300 to ≤600 mg, >600 mg	>150 to ≤300 mg	Safety

090177e18ef7c5fa\0.1\Draft\Versioned On:18-Jul-2018 10:23 (GMT)

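### Maximum daily dose over the whole dosing period is tested against later reactions and pain change, although both can help determine it, so a false dose relation can appear

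*SAP*

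**What the plan says.** - Section 5.4 lists "Daily dose (maximum" in six categories for both safety and efficacy. No period is attached to the maximum.
- Section 8.2.2 gives the only period for dosing: "Dosing period is from the day of initial dose in the survey to the day of last dose, including period of dose interruption".
- Section 2.1 lets dose respond to the patient's course: "The dose may be adjusted depending on age and symptoms as appropriate".
- Section 8.2.3.4 applies the 5.4 factors to this outcome: "number and proportion of patients with at least one adverse reaction occurring (initial onset) at >13 to ≤52 weeks will be tabulated and tests". It adds risk ratios and risk differences with 95% confidence intervals.
- Section 8.1.3 gives the test for ordinal factors: "Cochran-Armitage test (exact method) will be performed".
- Appendix A2.1 sets a reference category for maximum dose: "Reference populations for calculation of risk ratio and risk difference in subgroup analyses of safety are shown below".
- Section 8.2.4.6 compares pain change at Week 104, or at the end of treatment, across the same factor. Under 8.1.1 this is an analysis of covariance (ANCOVA) with the pre-treatment value as the only covariate.
- The only rule on repeated reactions is in 8.2.3.1 and works per preferred term (PT): "If the same adverse reaction (the same PT) occurs more than once in the same patient".
- Section 8.2.3.1 leaves out concomitant drugs started after first onset of the event. No such cut applies to dose.

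**The concern.** A maximum taken up to the last dose is known only after the outcomes can have occurred. A patient who reacts may never receive a later increase, and so stays in a lower category because of the reaction. A patient whose pain persists may receive more increases, and so enters a higher category because of poor response. Neither route needs any effect of dose on the outcome. A dose reduction does not lower a maximum already reached, so the safety route works only through increases that are withheld.

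Higher doses could then look safer in the any-reaction table and, with late titration, in the tested comparison. They could look less effective for pain. A significant factor triggers further tables by dose group, which carry the same distortion.

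For the tested safety outcome the direction depends on what initial onset means. Per PT, an early reactor can still count as a late event through a new PT, and the bias is mainly downward. Per patient, early reactors count as non-events, and the bias can go either way.

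**Working it through.** **The plan's own figure.** With 310 patients, the chance of seeing at least one reaction is 1 − (1 − 0.0097)^310 = 95.1% at 0.97% incidence and 1 − 0.99^310 = 95.6% at 1%. The number needed is ln 0.05 / ln(1 − 0.0097) = 307.3, so 308. The target of 310 reproduces and serves as the sample size below.

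**Assumed inputs (none are in the SAP).** No dose effect; 60% of patients due for an increase, at a median of 2, 4, 13 or 26 weeks; a reaction blocks later increases in 50% or 100%; 20% react by Week 13; later reaction hazard 0.15 or 0.3 per year. Population A is 310 patients on drug at Week 13, discontinuing at 0.4 per year. Population B follows the recruitment target in section 2.1: "A total of 310 patients with neuropathic pain who have been examined in the observation period of at least 52 weeks will be collected".

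**Mechanism in one scenario** (per PT, everyone followed to Week 104, hazard 0.3, median titration 13 weeks, full blocking, early reactions spread evenly over 13 weeks).

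- Late-event risk over 39 weeks: p = 1 − exp(−0.3 × 39/52) = 0.2015.
- If an increase is due, the chance that it has happened by week t is F(t) = 1 − 2^(−t/13). Averaged over onset times this is 0.782 for late reactors, 0.991 for patients without a late event (allowing for reactions after Week 52), and 0.279 for early reactors.
- P(higher dose | late event): a = 0.6 × (0.8 × 0.782 + 0.2 × 0.279) = 0.409.
- P(higher dose | no late event): b = 0.6 × (0.8 × 0.991 + 0.2 × 0.279) = 0.509.
- Risk in the higher group: pa / [pa + (1 − p)b] = 0.0824 / 0.4888 = 16.9%.
- Risk in the lower group: p(1 − a) / [p(1 − a) + (1 − p)(1 − b)] = 0.1191 / 0.5112 = 23.3%.
- Risk ratio 0.72, where the truth is 1. With median titration of 4 weeks the same formula gives a = 0.544, b = 0.552 and a risk ratio of 0.97.

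**Full range by null simulation** (risk ratios from 2,000,000 patients per scenario; rejection by the exact Cochran-Armitage test with three dose levels, n = 310, 1,000 runs per scenario). Ratios are higher versus lower maximum dose.

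| Outcome | A: risk ratio | B: risk ratio | Rejection at 5%, A / B |
|---|---|---|---|
| Any reaction (untested) | 0.44–0.93 | 0.42–0.95 | – |
| Tested outcome, per PT | 0.60–1.01 | 0.52–1.01 | 3–48% / 4–80% |
| Tested outcome, per patient | 0.75–1.19 | 0.65–1.18 | 3–14% / 3–37% |

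Per PT with median titration of 2–4 weeks, the risk ratio is 0.97–1.01 and rejection 3–6%. Rejection above 22% needs titration at 13–26 weeks and full blocking.

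**Sensitivity.** If 10% of reactors instead receive an increase, the ranges become 0.55–1.04 (any reaction), 0.65–1.12 (per PT) and 0.78–1.30 (per patient). With no blocking, per PT gives 0.99–1.14 in A and 0.99–1.01 in B. A different set of inputs (reaction risk 5–20%, chance of an increase 5–15% per 13 weeks after Week 13, asymptotic test) gives 13–99% rejection with the whole-period maximum and 3.6–5.5% with the maximum fixed by Week 13.

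**Pain** (ANCOVA of change on dose group and baseline; n = 310; 2,000 runs; baseline mean 6.5, SD 1.5; residual SD 2). If the odds of an increase rise 1.1 to 1.5 times per point of interim pain, the false difference is 0.15–1.0 points and rejection 10–99%. With no such dependence it is 0.0 points and 5–6%. With starting dose as the factor, even if it depends on baseline pain with the same odds, it is −0.01 to 0.01 points and 4–6%.

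**Day-91 maximum** (13 × 7 = 91, just before the tested window). Per PT: risk ratio 0.99–1.01, rejection 3–6%. Per patient: 1.05–1.16 and 4–8%; without early reactors, 0.99–1.01 and 3–6%.

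**The case against.** The strongest counter-argument is that the tested safety bias needs many first increases after Week 13. The only titration timing in the SAP (section 2.1) is an increase over a week or more, and with early titration the per-PT comparison is practically unbiased. That stands as a limit on size. The SAP does not exclude later increases, and the pain comparison does not depend on this point.

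Other points limit the claim without removing it:

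- Population B is a recruitment target. The safety analysis set in 5.1 requires no 52 weeks of treatment, so the figures for A are closer to the planned analysis.
- The lowest risk ratios belong to an untested table.
- The direction is not fixed: several ranges cross 1.
- The period for the maximum is inferred. It is the natural reading, since no other is given, but an undefined derivation is itself a gap.
- Section 4.1 calls the tests exploratory, and a significant result leads only to further tables. That answers concerns about error control; it does not make a biased estimate unbiased.
- Concomitant medications and non-medication therapies in 5.4 also have no time limit. That is a reason to look at them too, not to leave dose as it is.
- The version history records the survey as completed from version 6.0, so redefining a factor now has a post hoc cost.

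**Conclusion.** The concern holds. As written, the plan tests a dose factor that the outcomes can help determine, and it can report a dose relation where none exists. The safety bias ranges from negligible (early titration) to a per-PT risk ratio of 0.60 in patients on drug at Week 13, or 0.52 in those treated at least 52 weeks. The false pain difference can reach 1.0 point if increases follow interim pain strongly. These figures rest on assumed rates; they show what is possible, not the size in this survey. Given the exploratory status, the weight is minor to moderate, but the plan should be changed because a clean alternative is available at little cost.

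**What to change.** 1. In 8.2.3.4 and A2.1, for the tests, risk ratios and risk differences on reactions starting after Week 13 and up to Week 52, classify patients by maximum daily dose up to Day 91.
2. State in 8.2.3.4 whether initial onset is per PT or per patient. Only if it is per patient, limit the denominator for this factor to patients with no adverse reaction by Day 91, and footnote it.
3. In 8.2.3.4 and 8.2.4.6, show whole-period maximum dose descriptively, without P-value, risk ratio or risk difference. Keep starting dose, already in 5.4, as the tested dose factor for pain change.

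The cost is SAP wording and one variable derived from the administration records that section 9 already lists. The whole-period comparison loses its test and risk ratio. The Day-91 maximum ignores later increases: with median titration of 13–26 weeks, 16–29% of patients fall in the higher group, against 38–55% by whole-period maximum. Some bias remains if early reactors have twice the later hazard (per-PT risk ratio 0.92–0.98). The denominator limit, if needed, removes 0.20 × 310 = 62 patients when 20% react early. Because the survey is complete, record the change with its date and reason.
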